3.5.4.2 Aim 2: To test the feasibility, acceptability, and preliminary efficacy of the adapted intervention for stigma reduction, we will employ a randomized-controlled design in which we will randomize 80 Thai PLWH to two groups and follow them for 10 weeks.

3.5.4.2.1 Treatment group assignment: We propose to recruit 80 Thai PLWH who will be randomly assigned to either the Enhanced Treatment group (**ET**; $N=40$) or the Treatment-as-Usual group (**TAU**; $N=40$). While the ET group participants will receive the

proposed stigma reduction intervention, the TAU group participants will receive typical services available in the Sanpatong Hospital that are also available to the participants in the

Table 3: Sample Allocation for ET and TAU Groups (# in ET/ # in TAU)

Cisgender Straight Men	Cisgender Straight Women	MSM	Transgender	Substance User
8/8	8/8	10/10	5/5	9/9

ET group, including care co-ordination and linkage to public health nurses in local communities. Using a computer program, we will generate a list of random numbers to assign participants to either group. Numbered envelopes indicating condition assignment will be prepared and sealed. However, to ensure equivalence of gender/sexuality/substance use composition between study arms, we will stratify the sample and randomize each gender/sexuality/substance use category separately, so that each arm will consist of 40 participants with balanced gender/sexuality/substance use compositions. This balanced composition between groups will guarantee sufficient sample sizes for key subpopulations and, hence, enable subsequent analyses for possible heterogeneity of treatment effects. See **Table 3** for the sample allocation for both the ET and TAU groups. Study staff will not be aware of the assignment until the envelope is opened and the baseline survey has been performed.

3.5.4.2.2 Implementation: The stigma reduction intervention will consist of four group counseling sessions delivered by trained interventionists. In each session, a designated interventionist will meet with participants for 120 minutes in a designated room at the Sanpatong Hospital. To help build rapport among the group members, we will host, in total, 5 groups, including 1 group for cisgender straight men who are non-substance users ($n = 8$), 1 group for cisgender straight women who are non-substance users ($n = 8$), 1 group for MSM who are non-substance users ($n = 10$), 1 group for transgender individuals who are non-substance

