3.5.4.2.5 Measurement plans: As in our ongoing studies, structured instruments (see **Table 4**) will be used to assess Thai PLWH regarding their demographics, key clinical characteristics, and psychosocial factors addressed in the intervention, including stigma, attribution styles, physical and emotional arousals, karma beliefs, insights on sufferings, mindfulness, compassion, social support, and care engagement. The psychometric properties have been established for most of the instruments among Asian populations, in particular, in our ongoing R21 project. The survey will be available in the Thai language. The survey will have 250 items in total; however, there are multiple skip patterns. Depending on the responses of Thai PLWH, the survey may have as few as 160 items. These self-report measures will be conducted via Audio Computer-Assisted Self-Interview (ACASI) and will typically be completed within 30-40 minutes. Use of ACASI lessens the likelihood of socially desirable answers and minimizes data entry errors. Similar ACASI survey programs have proven successful in studies of participants with little or no prior computer experience in Asian populations.¹³⁹ Regarding care engagement measures, many studies have used single items to measure ART adherence, for example, gathering categorical data (*yes* or *no*) to measure whether patients achieved 95% adherence. However, in this project, we will create a latent variable for all these items to further control potential measurement errors.^{106,140-142} Viral load (VL) also be collected as an objective measure for adherence. The research staff in charge of data collection will be completely blind to treatment assignments of participants. Please note, our primary outcome is internal stigma, while our secondary outcomes are the indicators for care engagement, including self-reported adherence, viral load, self-reported patient engagement, and clinic visits.

Table 4: Measuring Instruments

Instrument	Items	Instrument description	Cronbach α
Demographic s and clinical outcomes	15	Participants are asked about their age, gender, race, ethnicity, education, income, health insurance, possible HIV transmission route, when they first learned of their HIV diagnosis, opportunistic infections and ART-taking status, morbidity, VL, and current CD4.	
Universal Cognitive-Behavioral components of HIV Stigma			

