Compassion	26	The Self-Compassion Scale ^{37,38} will be used to measure participants' kindness toward themselves during failure, perceiving one's experiences as part of the larger human experience, and holding painful thoughts and feelings in mindful awareness.	> .85
Care Engagement			
HIV medication Adherence	6	Participants will be presented with a list of current ART medications and questions to record their history of taking or stopping antiretroviral medication. The instrument will record their current ART regimen and reasons they stopped taking ART medications, where appropriate. Note that viral load will also be used as an objective measure of adherence.	0.96
3-day recall of ART adherence	1	This one-item visual analog scale is based on ¹⁵⁰ a 3-day adherence assessment. It accesses 3-day adherence along a continuum of "none of my doses" to "every one of my doses."	
30-day recall of ART adherence	1	This one-item visual analog scale ¹⁵⁰ assesses 30-day adherence, reported separately for each drug, along a continuum of "none of the doses" to "every dose." This scale has been shown to correlate with other adherence measures such as MEMS caps.	
Care Engagement	13	The Patient Activation Measure – Short Form will be used to measure participants' engagement in their care, as assessed by their agreement with statements about their beliefs in their active roles in care, confidence and knowledge to take action, capacity in taking action, and staying the course under stress. (Strong disagree : 1 to Strongly agree : 5)	0.88
Clinic Visits	2	How many missed visits over the past month? How many delayed visits over the past month?	

3.5.4.2.6 Timeline: The timeline for intervention sessions and data collection is summarized in **Table 5**. There are four data collection points: Week 1 (before intervention for enhanced treatment (ET) group), Week 4 (right after intervention for the ET group), Week 7, and Week 10. Therefore, in this data collection schedule, the ET group will have one-baseline (Week 1), one post-intervention evaluation (Week 4), and two follow-ups with 3-week intervals (Week 7 and Week 10). Assessment consists of a survey and a dried blood spot test at Weeks 1 and 4.

[figure not shown]
Table 5: Data Collecting Time Points

Time Points	Week 1	Week 2	Week 3	Week 4	Week 7	Week 8	Week 9	Week 10
ET Group	Intervention	Intervention	Intervention	Intervention				
	SV, VL			SV, VL	SV, VL			SV, VL
TAU Group								
	SV, VL			SV, VL	SV, VL			SV, VL

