3.5.4.2.7 A summary flowchart of the randomized waitlist-controlled trial

A flowchart is presented in **Figure 4** to summarize recruitment, enrollment, randomization, intervention delivery, and assessments. Please note that, for the ET group, the Week 1 assessment occurs right before the first intervention session, and the Week 4 assessment occurs right after the fourth intervention. In contrast, for the TAU group, there is no additional stigma reduction intervention, but the group will be assessed at Weeks 1, 4, 7, and 10. The same 3-week intervals will enable direct comparisons across conditions and assessments.

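### The clinic-visit outcome counts missed and delayed visits without asking how many HIV appointments were due and without excluding study sessions

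*Combined protocol and SAP*

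**What the plan says.** Section 3.5.4.2.5 (Measurement plans) states that "our secondary outcomes are the indicators for care engagement, including self-reported adherence, viral load, self-reported patient engagement, and clinic visits". In Table 4 the Clinic Visits row has two items: "How many missed visits over the past month? How many delayed visits over the past month". The plan gives no further definition of a visit and no scoring rule for these items. The nearest scoring statement, in the same section, is "we will create a latent variable for all these items to further control potential measurement errors". It follows a discussion of adherence items, and it is unclear whether it covers the visit items.

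Section 3.5.4.2.2 (Implementation) says: "The stigma reduction intervention will consist of four group counseling sessions delivered by trained interventionists". In each session the interventionist will "meet with participants for 120 minutes in a designated room at the Sanpatong Hospital", the hospital whose HIV clinics supply the participants (section 3.5.2). Section 3.5.4.2.7 adds that "for the TAU group, there is no additional stigma reduction intervention, but the group will be assessed at Weeks 1, 4, 7, and 10". That section also places the ET group's Week 1 assessment just before session 1 and its Week 4 assessment just after session 4. Section 3.5.4.2.8.2 defines the main treatment effect as β06, the arm difference in change from Week 1 to Week 4.

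**The concern.** Two separate weaknesses follow from the wording of the items.

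- **No denominator.** Both items are numerators. Someone with no appointment in the past month gives the same answer as someone who kept every appointment. For an individual, the score mixes engagement with how often the clinic happens to schedule that person.
- **No definition of a visit.** ET participants have four scheduled sessions at the hospital where they receive HIV care. One who misses a session, or comes late, could reasonably report it. TAU participants have no such sessions. Any such reporting would enter one arm only, mostly at the main time point, and would make ET look worse.

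The stakes are limited but real. Section 3.5.4.2.8.3 says interpretation will rest on the size and direction of effects, and section 3.5.4.3 uses effect sizes from this study to plan the next trial.

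**Working it through.** The plan states no figure for this outcome, so there is none to reproduce.

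**1. Is a visits-due item hidden elsewhere?** Section 3.5.4.2.5 gives a survey total of 250 items. Table 4, row by row: 15 + 10 + 16 + 48 + 47 + 4 + 52 + 9 + 26 + 6 + 1 + 1 + 13 + 2 = 250. The rows account for every item, and no row describes a count of appointments due.

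**2. Respondents with none due.** Appointment spacing is not given, so let it be *k* months (assumed). The share with none due in a one-month window is 1 − 1/*k*.

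| *k* (months) | None due | Of 80 |
|---|---|---|
| 1 | 0% | 0 |
| 2 | 50% | 40 |
| 3 | 67% | 53 |

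For illustration, suppose misses fall from 20% to 10% of due appointments. The difference per person-month is (0.20 − 0.10)/*k*, which is 0.10, 0.05 and 0.033. The ratio of the two means stays at 0.5 throughout (for example 0.033/0.067 at *k* = 3). The absolute contrast shrinks and fewer events support it, but its direction is unchanged.

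**3. ET sessions inside the recall window.** Table 5 places one session in each of Weeks 1 to 4. Taking these as days 0, 7, 14 and 21, the later assessments as days 21, 42 and 63, and a month as 28 to 31 days:

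| Assessment | ET sessions in window | TAU |
|---|---|---|
| Week 4 | 4 | 0 |
| Week 7 | 2 | 0 |
| Week 10 | 0 | 0 |

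At Week 1 no session has yet taken place, so adjusting for baseline through β06 would not remove an excess that appears at Week 4.

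These are upper limits on what could be missed. An ET participant assessed on schedule is on site for session 1 and probably for session 4, which leaves about two missable sessions at Week 4.

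**4. Possible excess in the ET count at Week 4.** Excess = missable sessions × share of sessions missed × share of respondents who count sessions as visits. The plan gives neither share. Assuming 10–25% of sessions are missed:

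| Share who count sessions | 4 missable | 2 missable |
|---|---|---|
| 2% | 0.008–0.02 | 0.004–0.01 |
| 5% | 0.02–0.05 | 0.01–0.025 |
| 20% | 0.08–0.20 | 0.04–0.10 |
| 100% | 0.40–1.00 | 0.20–0.50 |

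For scale, if 10% of due appointments are missed, the true count is 0.10/*k*, or 0.03–0.10 per person-month for *k* from 3 to 1. The excess therefore runs from well below the true count to many times above it, depending wholly on the assumed shares.

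**The case against.** The strongest reply has four parts.

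- **Zeros from people with none due do not bias the trial.** They arise in both arms, and stratified randomisation balances them in expectation. This stands. A reader might infer that the outcome is invalid for comparing the arms because it mixes engagement with appointment frequency. The design does not support that; the cost is precision.
- **Contamination by study sessions is not shown.** The row is headed as clinic visits and sits under care engagement. Table 4 summarises the instruments and may not give the full Thai wording. The plan also treats session attendance as a separate matter, logged for acceptability (section 3.5.4.2.8.1). This stands as far as it goes: contamination is possible, not established. But the item wording refers only to visits, no exclusion is stated, and no text uses the attendance log to check the visit items.
- **The sizes rest on assumptions.** This also stands. With 10% of sessions missed, four of them missable and half of respondents counting them, the excess is 0.20. That would reverse a true benefit of 0.10 at one-month spacing (−0.10 + 0.20 = +0.10). With 2% counting them, the result is −0.10 + 0.008 = −0.092, almost untouched. A reader might infer that a real improvement would be masked or reversed; the documents do not supply the rates needed to say so.
- **It is one secondary indicator of four in a pilot** that is not fully powered for efficacy. This lowers the priority. It does not remove the reason to fix wording that is cheap to fix.

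The latent-variable statement is no answer to the concern. Even if it covers these items, it supplies no denominator and does not address error that differs by arm.

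**Conclusion.** The point holds as a minor measurement weakness. It is certain that the outcome has no visits-due denominator and that the plan states no exclusion of study sessions. The first costs precision in both arms: about 0%, 50% or 67% of respondents would be uninformative in a given month at assumed spacings of 1, 2 or 3 months. The second opens a route to bias against ET at Week 4, smaller at Week 7 and gone by Week 10. Its size cannot be estimated, because the documents give no rates for missed sessions or for misreporting. It could not create a false benefit of ET. Internal stigma, which section 3.5.4.2.5 names as the primary outcome, is unaffected, as are feasibility and acceptability.

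**What to change.** - **Reword both items** to ask about *HIV clinic appointments, not counting study group sessions or study assessments*. Assessments belong in the exclusion because either arm could count a missed one.
- **Add one item** on the number of HIV clinic appointments scheduled in the same window.
- **Keep all randomised participants** in the intent-to-treat GEE of the reworded counts.
- **Report by arm and wave** the number of appointments scheduled and the number of participants with none due.
- **Present missed or delayed appointments out of those scheduled as a supportive analysis.** It should not replace the main one. Having an appointment scheduled is a post-randomisation variable that the intervention might change, so restricting to those participants gives up the randomised comparison. The report should say so.

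The cost is one more survey item on top of 250, two reworded items and a few lines in the analysis plan. The supportive analysis would include fewer participants per wave: about 80, 40 or 27 of 80 at assumed spacings of 1, 2 or 3 months.

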3.5.4.2.7 A summary flowchart of the randomized waitlist-controlled trial

A flowchart is presented in **Figure 4** to summarize recruitment, enrollment, randomization, intervention delivery, and assessments. Please note that, for the ET group, the Week 1 assessment occurs right before the first intervention session, and the Week 4 assessment occurs right after the fourth intervention. In contrast, for the TAU group, there is no additional stigma reduction intervention, but the group will be assessed at Weeks 1, 4, 7, and 10. The same 3-week intervals will enable direct comparisons across conditions and assessments.

3.5.4.2.8 STATISTICAL ANALYSIS PLAN

3.5.4.2.8.1 To evaluate feasibility and acceptability: **To evaluate feasibility**, defined as the participation rate among eligible Thai PLWH, we will carefully document in study logs the numbers of Thai PLWH who are eligible to participate, approached by staff, willing to participate, and eventually enrolled in the study. **We will assess acceptability**, defined as the study completion rate, with detailed documentation of their attendance in intervention sessions, and program completion or termination. We will record their reasons for non-participation and early termination. The numbers of prompts and reminders needed to ensure participation will also be recorded. To further shed light on factors contributing to intervention acceptability, we will triangulate the study logs with an extensive structured post-intervention *exit interview*, which will probe participants about their opinions on different aspects of the adapted intervention, including relevance, delivery, and satisfaction with the activities and materials. At the end of the exit interview, any improvements that participants suggest to enhance the efficacy of the intervention in helping Thai PLWH more effectively manage their family relations and illness will be documented and implemented. All the exit interviews ($N=40$) will also be audio-recorded and transcribed. Standard qualitative coding and theme-extracting approaches as described in Section 3.5.4.1.1 will be applied to identify areas for further improvement. Finally, the interventionists will keep detailed progress notes for each session, documenting which topics and activities were covered in the sessions as well as Thai PLWH's patterns of participation. These progress notes will be triangulated with transcriptions of intervention session audio-recordings and with the exit interviews to identify active intervention components and assess their acceptability. Participants' health outcomes as a result of the stigma reduction intervention, along with their responses regarding its feasibility and acceptability, will allow us to better understand ways to assist Thai PLWH in managing their relationships and their HIV, improving their well-being, and contributing to overall health and containment of the HIV epidemic.

3.5.4.2.8.2 To evaluate preliminary efficacy: Our study design involves a two-group randomized-controlled clinical trial with four assessments for each participant and a total of 320 observations. **The study is not fully powered for efficacy, limiting the sophistication of the analyses we can conduct to test efficacy.** However, to obtain robust estimations, we will take the following steps: (a) we will examine the scope and mechanisms for missing data and attrition to investigate the extent to which the missing-at-random (MAR) assumption is violated, and, if it is violated, we will adapt procedures recommended by Barnes et al.;¹⁵¹ (b) we will examine all measures at each observation time using univariate statistics to identify potential irregular response patterns and determine overall quality of data; (c) we will assess scale reliability and compare it to published psychometrics in comparable populations; (d) we will triangulate objective and self-report measurement of adherence; (e) we will give special attention to our key primary outcome variables (quality of life and objective health measures) as well as secondary outcome variables (stigma, disclosure preparedness, family relations, family support, self-management efficacy, adherence, depressive and anxiety symptoms, and physical symptoms; note that all the outcomes are continuous); and (f) we will investigate the quality of random assignment by conducting a series of bivariate statistics comparing selected demographic, clinical, and psychosocial factors between treatment groups at baseline. Important findings may result in the modification of subsequent analyses.

[figure not shown]
We will use Generalized Estimating Equations (GEE) to test the proposed hypotheses while controlling for stratification and basic demographic backgrounds. This GEE framework allows us to carry out statistical tests for all the major hypotheses by comparing "population averages" between groups while appropriately adjusting for autocorrelations in observations due to repeated measures for the same groups of participants. We will further apply the small-sample estimator of variance to accommodate our sample size.¹⁵² To compute

standard errors and confidence intervals for statistical inferences, we will use a clustered sandwich estimator to obtain robust estimations. Note that, for simplicity of the exposition, controlling variables are not shown in the equations. All the statistical testing will be analyzed with the statistical software packages Stata and R. **Please note, our interpretations will focus on the size of the between-group effect and its replication in the DT group because this study is not designed to have power to detect small effects.**

We will fit the following GEE intent-to-treat model with the Thai

PLWH: $g(E(Y_{it})) = \beta_{01} + \beta_{02} * Week_{i4} + \beta_{03} * Week_{i7} + \beta_{04} * Week_{i10} + \beta_{05} * I(ET_i) + \beta_{06} * I(ET_i) * Week_{i4} + \beta_{07} * I(ET_i) * Week_{i7} + \beta_{08} * I(ET_i) * Week_{i10}$ where $g(\cdot)$ denotes a proper link function; Y_{it} denotes primary or secondary outcomes in separate models for participant i at Week t ; $t = 1, 4, 7$, and 10 ; and $I(ET_i)$ denotes a binary variable indicating whether participant i belongs to the immediate treatment group. In this model, β_{01} represents the mean

outcome levels for DT at Week 1; β_{02} represents the slope for TAU between Week 1 and Week 4; β_{03} represents the slope for DT between Week 1 and Week 7; β_{04} represents the slope for TAU between Week 1 and Week 10; β_{05} represents the average group difference in outcomes between TAU and ET groups at Week 1; β_{06} represents the average group difference in the slope between TAU and ET groups between Week 1 and Week 4; β_{07} represents the average group difference in the slope between TAU and ET groups between Week 1 and Week 7; and β_{08} represents the average group difference in the slope between TAU and ET groups between Week 1 and Week 10. We define that the main between-group treatment effect is equal to β_{06} ; therefore, we expect that β_{06} will be significantly different from 0.

3.5.4.2.8.3 Sample Size Considerations: As the goal of qualitative components is to explore a range of experiences among Thai PLWH's experiences in family relations and self-management, as well as their opinions regarding acceptability of the adapted intervention, it is critical to include participants with a wide enough range of experiences to reach conceptual saturation. Although "saturation" and "a priori determined sample size" have stimulated debates in the literature,¹⁵³⁻¹⁵⁵ it is generally agreed that a sample size of 30 participants should be sufficient to capture a range of experiences.¹⁵⁴ Therefore, the 30 in-depth interviews we utilize in our AIM 1 to revise the conceptual model, as well as the 40 exit interviews we will conduct in our AIM 2 to evaluate acceptability of the intervention, should provide sufficient saturation and guide future intervention revisions. Please note, we do not intend to fully power the quantitative data to formally test the model in this project. Rather, we will focus on the magnitude and valence of the treatment effect as well as its overall pattern during replication. However, in order to understand the size of the difference in slopes (β_{06}) between treatment groups our data can detect given our sample size, observation time points and the GEE model, we used the *liu.liang.linear.power* function in the *longpower* package¹⁵⁶ in the R statistical software and supplied with the preliminary data from our ongoing R21 project. The results are illustrated in **Figure 5**. Given our study designs with $N = 80$ and model choice (GEE), we can detect as small as 2.4 in β_{06} with 80% power.

3.5.4.3 **Aim 3: To revise and finalize the study protocols using results from AIM 1 and AIM2.**

The study protocols have two parts, including intervention protocol and operational protocol. The intervention protocol is the intervention manual providing a detailed, step-by-step guide for each of the intervention sessions. The goals, topics, intervention approaches, and timeframe for each module will be clearly delineated. We will use the study results from AIM 2—the feasibility, acceptability, and effect sizes—to finalize the intervention protocol. Since our intervention will be adapted using the qualitative data from our prior studies with additional input from stakeholders, we expect most intervention components will be feasible and acceptable to our participants; yet, by using the qualitative data from exit interviews and study logs, we will identify specific intervention components in need of revision, and particularly those clearly not acceptable to Thai PLWH. To further increase feasibility and acceptability of the intervention, we will recommend additional

adjustments to the intervention and submit them to the CAB and SAB for final review. We will calculate power and required sample size of the future R01 study using the preliminary effect sizes from the current project.

The operation protocol, in contrast, will address a series of necessary activities for the success of the subsequent R01 study. We will adapt an existing operation protocol from a similar project conducted by the PI in her K award as described in Section 3.3.2. In that project, the PI and the research team developed an operation protocol and successfully set up a preliminary randomized controlled trial to test efficacy of a family-centered self-management intervention for Chinese women living with HIV in China. The operation protocol will include topics such as project set-up, required facilities, inclusion and exclusion criteria, participation recruitment and retention, random assignment procedures, training materials and supervision, intervention fidelity, data collection and storage, data quality assurance, arrangement of clinical referrals for participants with mental illness, reporting of potential harm to others or themselves, timeline and important dates, and tasks and duties for personnel, among others. To refine our operation protocol so that it can cover as many diverse conditions as possible, **we will further collect data from all stages of the research implementation and keep detailed logs of all the study activities**. In this documentation, study staff will be instructed to detail not only what has happened according to the study plans but also unexpected situations that may facilitate or impede the designed activities. During regular supervision with Drs. [name], [name], [name], and [name], this documentation will be reviewed and discussed thoroughly within the team members. Special attention will be given to participant recruitment and retention, and we will enlist several strategies to handle different situations and to engage participants. The feasibility data from the recruitment and retention study logs will be analyzed to identify barriers for Thai PLWH to partake and be retained in the study. Solutions to these potentially emerging problems will be brainstormed and implemented to test their effectiveness. The study team will also review related literature to identify best practices. Indeed, we previously published a study on building cross-cultural HIV research collaborations using these administrative research documents⁹³ and made recommendations for selecting approaches that may help forge healthy international HIV research collaborations. Finally, the CAB members will review different drafts of the protocol and provide feedback for further improvement.

Although this current R34 study will be implemented at the Sanpatong Hospital, **we will actively involve stakeholders in the local area**. We have successfully collaborated with the researchers affiliated with the Sanpatong hospital and other service organizations in the local network of HIV care and have developed local CABs and SABs consisting of local Thai PLWH community members, service providers and experts from the areas. From the beginning of the R01 project, we will host CAB and SAB meetings on a regular basis. During the meetings, Drs. [name], [name], [name], and [name] will report study progress, submit documents for review, and discuss topics that need input from the CAB and SAB. The CAB and SAB will share responsibilities in overseeing the project, helping interpret qualitative data arising from the study activities, reviewing intervention adaptation, and finalizing study protocols. We will compare the perspectives from the CAB and SAB and integrate them into the final protocols. The final intervention and operation protocols will be approved by the CAB and SAB, which represent all partner agencies.
